- Contraindication to rabies vaccination (*Rabipur* is contraindicated in subjects with an history of a severe hypersensitivity to any of the ingredients in the vaccine. Note that the vaccine contains polygeline and residues of chicken proteins, and may contain traces of neomycin, chlortetracycline and amphotericin B) (Refer to the [*Rabipur* SmPC, 2010]).
- Major congenital defects.

- Serious chronic illness.
- Children with a past history of a neurological disorder or atypical febrile seizure (a febrile seizure is atypical if it meets one of the following criteria: not associated with fever; lasts > 5 minutes; focal (not generalized); followed by transient or persistent neurological abnormality; occurs in a child < 6 months of age).
- Acute disease and/or fever at the time of enrolment.
 - Fever is defined as temperature $\geq 37.5^{\circ}\text{C}/99.5^{\circ}\text{F}$ for oral, axillary or tympanic route, or $\geq 38.0^{\circ}\text{C}/100.4^{\circ}\text{F}$ for rectal route.
 - Subjects with a minor illness (such as mild diarrhea, mild upper respiratory infection) without fever may, be enrolled at the discretion of the investigator.
- Administration of immunoglobulins and/or any blood products during the period starting three months before the first dose of study vaccine or planned administration during the study period.
- Moderate or severe malnutrition at screening defined as weight for age or weight for height Z-score < -2 .
- Hemoglobin concentration $< 8 \text{ g/dl}$ at screening.
- Same sex twins (to avoid misidentification).
- Maternal death.
- Prior receipt of an investigational malaria vaccine.

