 - The occurrence of solicited local and general AEs in the first 50 subjects enrolled in each group within four days (day of vaccination and three subsequent days) after Dose 3 of study vaccine (all groups including controls), after Dose 4 (groups R012-20, R012-14-mD, Fx012-14-mFxD and Fx017-mFxD), after Dose 5 (groups R012-14-mD, Fx012-14-mFxD and Fx017-mFxD) and after Dose 6 (groups R012-14-mD and Fx012-14-mFxD).

11.3. **Tertiary endpoints**

- **Immunogenicity**
 - Anti-CS antibody avidity at specified timepoints.

11.4. **Determination of sample size**

For the primary endpoint, demonstrating incremental vaccine efficacy against clinical malaria of a fractional dose schedule over the standard schedule, the study has at least 90% power to show a significant incremental vaccine efficacy (lower limit of 95% CI above 0), assuming 250 evaluable subjects per group and an incidence of at least 0.5 episodes/person year at risk (pyr) in the Control group, 0.29 episodes/pyr in the standard schedule groups and 0.16 episodes/pyr in the fractional dose schedule. This corresponds to an incremental efficacy (1-Hazard Rate) of 50% of the fractional dose schedule over the standard schedule. The primary endpoint compares the R012-20+R012-14-mD groups versus the Fx012-14-mFxD group (2:1). For secondary endpoints evaluating efficacy against *P. falciparum* infections, it is anticipated that incidence of infection in the study will be higher than incidence of clinical malaria resulting in adequate power.

In this study the reactogenicity (solicited local and general AEs) and the biochemistry and hematology parameters will be evaluated in a sub-cohort consisting of the first 50 subjects enrolled in each group (total 250 subjects). The anti-CS and anti-HBs immune responses will be tested in a subset consisting of the first 50 subjects enrolled in each group (total 250 subjects); see the [glossary of terms](#) for the definitions of subset and sub-cohort.

Assuming a post-vaccination anti-CS GMC of approximately 50 IU/ml for the fractional dose schedules and a log SD of 0.5 the precision obtained by 95% CIs of the GMC with a sample size of 50 subjects per group is (36.3-68.8).

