- The concentration of biochemistry (ALT, creatinine) and hematology (hemoglobin, WBC, platelets) parameters in the first 50 subjects (25 subjects per site) enrolled in each group (reactogenicity sub-cohort) before Dose 3, seven days post-Dose 3 and 30 days post-Dose 3.

• Reactogenicity (reactogenicity sub-cohort)

The occurrence of solicited local and general AEs in a the first 50 subjects enrolled in each group within four days (day of vaccination and three subsequent days) after Dose 3 of study vaccine (all groups including controls), after Dose 4 (groups R012-20, R012-14, Fx012-14 and Fx017-20), after Dose 5 (groups R012-14, Fx012-14 and Fx017-20) and after Dose 6 (groups R012-14 and Fx012-14).

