7.1. Demography

7.1.1. Analysis of demographics/baseline characteristics planned in the protocol

A study flow diagram (consort) will be generated to present the number of subjects screened, randomized, receiving doses and included in the PPS analyses.

Demographic characteristics (age and gender) and the baseline hemoglobin level will be tabulated per study group overall, and by site, for each cohort (ES, PPS cohort for efficacy and PPS cohort for immunogenicity).

The mean age at first vaccination (in months) (plus range and standard deviation [SD]) of the vaccinated subjects as a whole, and per group, will be calculated.

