The percentage of subjects reporting an SAE (all, fatal, related) from Dose 1 (Day 0) until Month 14, from Day 0 until Month 21, from Day 0 until Month 26, from Day 0 until Month 33 and over the whole study duration (Dose 1 [Day 0] until Month 50), classified by the MedDRA preferred term level, will be tabulated with exact 95% CI.

The percentage of subjects reporting an AE or SAE leading to withdrawal from further vaccination from Dose 1 (Day 0) until Month 50, classified by the MedDRA preferred term level, will be tabulated with exact 95% CI.

The percentage of subjects reporting severe malaria cases and cerebral malaria cases from Day 0 up to Month 14, Day 0 up to Month 21, Day 0 up to Month 26, Day 0 up to Month 33 and Day 0 up to Month 50 and over successive years within the study will be tabulated with exact 95% CI.

The percentage of subjects reporting pIMDs from Day 0 up to Month 14, Day 0 up to Month 21, Day 0 up to Month 26, Day 0 up to Month 33 and Day 0 up to Month 50, classified by the MedDRA preferred term level will be tabulated with exact 95% CI.

The percentage of subjects reporting meningitis from Day 0 up to Month 14, Day 0 up to Month 20, Day 0 up to Month 26, Day 0 up to Month 32 and Day 0 up to Month 50 classified by the MedDRA preferred term level will be tabulated with exact 95% CI.

The percentage of subjects reporting seizures occurring within 30 days (day of vaccination and 29 subsequent days) after each dose of study vaccine, classified by the MedDRA preferred term level will be tabulated with exact 95% CI.

For generalized convulsive seizures occurring within seven days following a dose of study vaccine, an analysis will be performed based on the Brighton Collaboration guidelines [Bonhoeffer, 2004]. This includes descriptive tables of the time relationship of seizures to vaccination, the duration of seizures and the level of diagnostic certainty.

Biochemistry (ALT, creatinine) and hematology (hemoglobin, WBC, platelets) values that are outside of the reference ranges (see protocol section 7.5.2.1) will be described for the reactogenicity sub-cohort (first 50 subjects enrolled in each group) before Dose 3, seven days post-Dose 3 and 30 days post-Dose 3. Frequency distribution of results by toxicity grades will be tabulated by group.

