7.5.2.1. Clinical Safety Laboratory Investigations

For the analysis of hematology and biochemistry parameters, the following grading scale will be used:

Test	Acceptable limit/Normal range	Grade 1	Grade 2	Grade 3	Grade 4
Hemoglobin	≥ 8.0 g/dl	> 8.0 to 6.0 g/dl	> 6.0 to 5.0 g/dl	< 5.0 g/dl	< 5.0 g/dl and clinical signs of heart failure
WBC	≥ 4.0 x10³/µl < 17 x10³/µl	2.5 to 4.0 x 10 ³ /µl	1.5 to 2.4 x 10 ³ /μl	1.0 to 1.4 x 10 ³ /µl	< 1.0 x 10 ³ /μl
Platelets	≥ 100 x10³/µl	50 to 99 x 10 ³ /μl	25 to 49 x 10 ³ /μl	< 25 x 10³/µl	< 25 x 10 ³ /µl and clinical signs of bleeding
ALT	≤ 60 IU/L	1.1 to 2.5 x ULN	2.6 to 5.0 x ULN	5.1 to 10.0 x ULN	> 10.0 x ULN
Creatinine	≤ 60 µmol/L (or 0.6 mg/dl)	1.1 to 1.5 x ULN	1.6 to 3.0 x ULN	3.1 to 6.0 x ULN	> 6.0 x ULN or requires dialysis

ALT = alanine aminotransferase; ULN = upper limit of the normal range; WBC = white blood cells Grading scale adapted from: [NIAID, 2004] Division of AIDS table for grading the severity of adult and pediatric adverse events, December 2004.

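### The laboratory safety endpoint is five concentrations, but the plan specifies only out-of-range values and toxicity grades, so neither the concentrations nor the within-child change from pre-Dose 3 is estimated

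*SAP*

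**What the plan says.** Group names below are the SAP's.

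- **Endpoint.** SAP 5.2 lists "The concentration of biochemistry (ALT, creatinine) and hematology (hemoglobin, WBC, platelets) parameters in the first 50 subjects (25 subjects per site) enrolled" in each group, at three times: before Dose 3, and 7 and 30 days after it. Protocol 11.2 has the same endpoint. The matching objective (protocol 2.2, SAP 3.2) is to assess safety on these parameters.
- **Analysis.** SAP 7.5.1 says that out-of-range values will be described at the three times, and that "Frequency distribution of results by toxicity grades will be tabulated by group". Protocol 11.10 says the same. SAP 7.5.2.1 adds only the grading scale, and SAP 10 lists no change on this point.
- **Size.** 50 children per group, 250 in all (protocol 11.4).
- **Other haemoglobin summary.** Under demographics, "the baseline hemoglobin level will be tabulated per study group overall, and by site" (SAP 7.1.1). The only haemoglobin sample taken from every child at entry is the screening one.
- **Thresholds.** Haemoglobin of 8.0 g/dl or more is within the acceptable range (protocol Table 29, SAP 7.5.2.1). A value below 8 g/dl at screening was an exclusion (protocol 5.3).
- **Timing.** Fx017-20 is sampled at Month 7, Month 7 plus 7 days and Month 8. All other groups are sampled at Month 2, Month 2 plus 7 days and Month 3 (protocol Table 21).

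**The concern.** The endpoint is continuous and the samples are paired: the same children are bled before and after Dose 3. The specified analysis reduces each result to a grade or an in-range/out-of-range flag and does not link the before and after values. A shift across a whole arm after a full or fractional third dose is then seen only through the children who cross a cut-off.

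The SAP handles other concentrations differently. For antibody concentrations in the same children (the immunogenicity subset is the reactogenicity sub-cohort, protocol 6.2.3), SAP 7.4.1 and 7.4.2 plan geometric means, 95% confidence intervals and full distribution curves.

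At stake is one secondary safety objective. The trial compares third-dose schedules, and on these five parameters the plan as written gives no estimate of level, change or difference.

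**Working it through.** **1. The plan's own precision figure.** The documents give no precision or power figure for laboratory values. The only one for groups of 50 is the anti-CS interval in protocol 11.4: 50 × 10^(±1.96 × 0.5/√50) = 50 × 10^(±0.1386) = 36.3 to 68.8. It reproduces.

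**2. Assumptions.** Haemoglobin mean and SD are not in the documents. I take a mean of 10.0, 10.5 or 11.0 g/dl, an SD of 1.0, 1.2 or 1.5, a normal distribution, and a fall of 0.5 or 1.0 g/dl in one of two arms of 50. The model ignores the screening exclusion, which would tend to lower the counts below 8.0. The other four parameters were not modelled.

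**3. Formulas.**
- Expected children below 8.0 = 50 × Φ((8.0 − mean + fall)/SD). At mean 10.5 and SD 1.2: with no fall, 50 × Φ(−2.083) = 0.93; after a 0.5 fall, 50 × Φ(−1.667) = 2.39.
- Graded summary: exact power of Fisher's test on below 8.0, two-sided 5%.
- Means: two-sample t-test on the post-dose value. The standard error is SD × √(2/50) = 0.2 × SD, so the 95% half-width is 1.984 × 0.2 × SD = 0.40, 0.48 or 0.60 g/dl.

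**4. Results.**

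| Mean | SD | Below 8.0, no fall | Below 8.0, 0.5 fall | Fisher | t-test | Below 8.0, 1.0 fall | Fisher | t-test |
|---|---|---|---|---|---|---|---|---|
| 10.0 | 1.0 | 1.1 | 3.3 | 4% | 70% | 7.9 | 53% | 99.9% |
| 10.0 | 1.2 | 2.4 | 5.3 | 8% | 54% | 10.1 | 54% | 98.5% |
| 10.0 | 1.5 | 4.6 | 7.9 | 10% | 38% | 12.6 | 48% | 91% |
| 10.5 | 1.0 | 0.3 | 1.1 | 0.1% | 70% | 3.3 | 9% | 99.9% |
| 10.5 | 1.2 | 0.9 | 2.4 | 1% | 54% | 5.3 | 23% | 98.5% |
| 10.5 | 1.5 | 2.4 | 4.6 | 5% | 38% | 7.9 | 30% | 91% |
| 11.0 | 1.0 | 0.1 | 0.3 | <0.1% | 70% | 1.1 | 0.1% | 99.9% |
| 11.0 | 1.2 | 0.3 | 0.9 | <0.1% | 54% | 2.4 | 2% | 98.5% |
| 11.0 | 1.5 | 1.1 | 2.4 | 1% | 38% | 4.6 | 13% | 91% |

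For a 0.5 g/dl fall the smallest gap between the two summaries is 38 − 10 = 28 percentage points (mean 10.0, SD 1.5). With 0 of 50 below 8.0 in one arm, 5 of 50 in the other gives Fisher p = 0.056 and 6 of 50 gives p = 0.027.

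**5. Using the pre-dose value.** The SD of change is SD × √(2(1 − r)). At an assumed correlation r of 0.5 it equals the SD, so change scores gain nothing. At r = 0.7, power for a 0.5 g/dl fall rises to 90%, 77% and 58% at SD 1.0, 1.2 and 1.5.

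**The case against.** - **No laboratory test is planned.** SAP 8 makes all secondary endpoints descriptive apart from one hierarchical efficacy comparison. Fisher's test is therefore not the plan's method. This stands: the powers only compare how sensitive the two summaries are.
- **The size rests on assumed values.** This stands. A reader might infer that a clear haemoglobin fall would leave almost no trace. The documents do not support that. At mean 10.0 and SD 1.2, a 1.0 g/dl fall takes the expected count below 8.0 from 2.4 to 10.1 of 50, which a grade table would show.
- **The screening threshold does not fix the starting point.** A reader might infer that nearly every child is ungraded before Dose 3. But screening precedes Day 0, the pre-Dose 3 sample comes at Month 2 or Month 7, and transmission is mid to high (protocol 1.2.1). Anaemia can develop in between.
- **Other routes exist.** Abnormal results judged clinically significant become AEs or SAEs (protocol 9.1.4). That route depends on judgement about the individual child and cannot show a modest shift across an arm. The list of tables (SAP 11.2) is held outside these documents and may contain more. So one can say that the SAP does not specify the summaries, but not that they will never be produced.
- **Fx017-20 has no concurrent comparator.** This stands. Protocol 1.2.2 itself warns of seasonal bias when periods differ (there, for malaria incidence), and season and age also differ here. Adjusting for the pre-dose value does not remove that.

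**Conclusion.** The mismatch holds on the documents alone: the endpoint is a set of concentrations, and the specified analyses are out-of-range values and grades. Following the text leaves the endpoint and the within-child change unestimated.

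The size is conditional and covers haemoglobin only. Over the assumed means and SDs, a 0.5 g/dl fall has Fisher power of at most about 10% on the graded summary, against about 38 to 70% for an unadjusted comparison of means. For a 1.0 g/dl fall the graded figure runs from about 0.1% (mean 11.0, SD 1.0) to 54% (mean 10.0, SD 1.2), so such a fall may be visible if the mean is near 10. A reader might extend the result to ALT, creatinine, WBC and platelets. The mismatch applies to all five parameters, but these figures do not.

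The point does not touch the primary objective. It is a gap in one secondary safety analysis that can be closed cheaply.

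**What to change.** In SAP 7.5.1, keep the grade tables and add:

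1. For each parameter, group and time point: n, mean (geometric mean for ALT and creatinine), SD, median, and the change from pre-Dose 3 with a 95% CI.
2. Descriptive differences in change at 7 and 30 days, adjusted for the pre-Dose 3 value and site, with 95% CIs, only for groups sampled at the same time: Fx012-14 versus pooled R012-20 + R012-14, and R012-20, R012-14 and Fx012-14 each versus Control.
3. Fx017-20 within group only, with a note that it is sampled at Months 7 to 8.

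Separately, SAP 7.5.2.1 prints haemoglobin Grade 1 as "> 8.0 to 6.0 g/dl". This conflicts with the normal range in the same row (8.0 and above) and with 7.9 to 6.0 in protocol Table 29. The grade table depends on this cut-off, so the passages must be reconciled.

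**Cost.** A few descriptive tables from data already collected, with no new samples and no alpha spent. Item 2 gives 4 contrasts × 5 parameters × 2 time points = 40 intervals unadjusted for multiplicity. About 0.05 × 40 = 2 would exclude no difference by chance, and the text should say so.

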7.5.2. Additional considerations

Note that the study will be converted in CDISC. Accordingly Day 0-Day N will be replaced by Day 1-Day N+1 for the statistical analysis.

7.5.2.1. Clinical Safety Laboratory Investigations

For the analysis of hematology and biochemistry parameters, the following grading scale will be used:

Test	Acceptable limit/Normal range	Grade 1	Grade 2	Grade 3	Grade 4
Hemoglobin	≥ 8.0 g/dl	> 8.0 to 6.0 g/dl	> 6.0 to 5.0 g/dl	< 5.0 g/dl	< 5.0 g/dl and clinical signs of heart failure
WBC	≥ 4.0 x10³/µl < 17 x10³/µl	2.5 to 4.0 x 10 ³ /µl	1.5 to 2.4 x 10 ³ /μl	1.0 to 1.4 x 10 ³ /µl	< 1.0 x 10 ³ /μl
Platelets	≥ 100 x10³/µl	50 to 99 x 10 ³ /μl	25 to 49 x 10 ³ /μl	< 25 x 10³/µl	< 25 x 10 ³ /µl and clinical signs of bleeding
ALT	≤ 60 IU/L	1.1 to 2.5 x ULN	2.6 to 5.0 x ULN	5.1 to 10.0 x ULN	> 10.0 x ULN
Creatinine	≤ 60 µmol/L (or 0.6 mg/dl)	1.1 to 1.5 x ULN	1.6 to 3.0 x ULN	3.1 to 6.0 x ULN	> 6.0 x ULN or requires dialysis

ALT = alanine aminotransferase; ULN = upper limit of the normal range; WBC = white blood cells Grading scale adapted from: [NIAID, 2004] Division of AIDS table for grading the severity of adult and pediatric adverse events, December 2004.

7.5.2.2. Concomitant Medication and Concomitant Vaccination

Medications will be coded using the GSKDRUG dictionary.

The frequencies and percentages of subjects reporting antipyretic medications (administered during seven days following each dose of study vaccine, Day 0 to Day 6) will be tabulated by vaccine group for each study dose and across doses. All concomitant medication will be provided in individual listings.

Antipyretics will be further considered prophylactic when administered in the absence of ANY symptom and in anticipation of a reaction to the vaccination.

Concomitant vaccinations administered in the period starting seven days before the first dose of study vaccines and ending at the last study visit (Day -7 to Month 50) will be listed.

7.5.2.3. Additional analysis for severe malaria

A listing for severe malaria cases with associated sign and symptoms will be provided. The same listing will be provided for cerebral malaria cases.

8. ANALYSIS INTERPRETATION

Vaccine efficacy estimates with a lower limit of the 95% CI above 0 are to be considered statistically significant.

If the standard schedule of 3 full doses at month 0, 1 and 2 is not statistically significantly superior to the control group in terms of efficacy, the other secondary objectives should be interpreted in the light of this finding.

In order to control alpha not only for the primary objective but also for the secondary objective of incremental efficacy over the 12-month period post-dose 3 of a schedule with a fractional dose at month 7 versus 3 full doses, a sequential approach will be implemented (hierarchical testing). The endpoints will be analyzed sequentially and any conclusion on the secondary endpoint will be conditional to reaching the primary endpoint. All other secondary endpoints should be interpreted descriptively.

9. CONDUCT OF ANALYSES

9.1. Sequence of analyses

All analyses (including interim analyses) will be conducted on data as clean as possible.

- Sequence of analyses and conditional continuation:
 - A first analysis will be performed on data collected up to Month 21 (Visit 25) to evaluate the primary objective (cleaned data) and relevant secondary objectives.
 - A second analysis will be performed on data collected up to Month 33 (Visit 31) to evaluate relevant secondary objectives.
 - A final analysis will be performed at study end (Month 50) on data collected up to Month 50. An integrated study report presenting all results until Month 50 will be produced.
- After the interim analyses, the Independent Data Monitoring Committee (IDMC) will have the possibility to recommend the suspension of further vaccinations and termination of specific study group(s) upon consideration of the study results. In the event that the IDMC recommend the suspension of further vaccinations, the group(s) impacted will be followed up for 12 months after their last study vaccination.

Description	Disclosure Purpose (CTRS=public posting, SR=study report, internal)
Final analysis E1_01	SR, CTRS
Analysis M21 E1_02	SR, CTRS
*Analysis M33 E1 03	CTRS

^{*}The need for a SR will be evaluated at a later time point depending on regulatory need.

9.2. Statistical considerations for interim analyses

The analysis of the primary endpoint will be performed after Month 21 (Visit 25) on cleaned data collected up to Month 14. No alpha adjustment is foreseen because final analysis of the primary endpoint will occur at the time of the first interim analysis after Month 21 (Visit 25) on cleaned data collected up to Month 14. Data up to Month 21 (Visit 25) will also be as clean as possible.

10. CHANGES FROM PLANNED ANALYSES

The Total Vaccinated Cohort and the According To Protocol cohort have been renamed Exposed Set (ES) and Per-Protocol Set (PPS) respectively.

The seropositivity threshold for anti-CS has been updated from 0.5 EU/ml to 1.9 EU/ml.

A Solicited Safety Set has been added in the analysis set section to fit with the new statistical rules and layouts applicable from the 12th of November 2018.

For purposes of analyses and to simplify the naming convention of the groups in Figure 1 haven been simplified. The label names of the study groups have been renamed according to the following table:

Vaccination schedule	Group label in protocol	Group label in SAP
RTS,S/AS01 _E full dose given at Month 0, Month 1, Month 2 and a fourth dose at Month 20	R012-20	R012-20
RTS,S/AS01 _E full dose at Month 0, Month 1, Month 2, an early fourth dose at Month 14 and yearly full doses at Month 26 and Month 38	R012-14-mD	R012-14
RTS,S/AS01 _E full dose at Month 0 and Month 1, RTS,S/AS01 _E fractional dose (1/5 th dose) at Month 2 and yearly fractional doses at Month 14, Month 26, Month 38	Fx012-14-mFxD	Fx012-14
RTS,S/AS01 _E full dose at Month 0 and Month 1, RTS,S/AS01 _E delayed fractional third dose (1/5 th dose) at Month 7 and yearly fractional doses at Month 20 and Month 32	Fx017-mFxD	Fx017-20
Rabies vaccine at Month 0, Month 1 and Month 2	Control	Control

A sequential approach to the analysis of incremental efficacy over the 12-month period post-dose 3 of a schedule with a fractional dose at month 7 versus 3 full doses was implemented (see section 8).

204889 (Malaria-094) Statistical Analysis Plan

The following analyses were added or modified:

- Unsolicited adverse events within 7 days after each vaccination will be described in addition to the 30 days analysis
 - Analyses on the occurrence of PIMDs (described in section Secondary endpoints) were added in section Analysis of safety and reactogenicity planned in the protocol, as they were missing in the protocol
- Secondary endpoint for efficacy
 - Analyses considering different calendar follow-up time was updated. In the protocol an indirect comparison was suggested taking into account incidence in controls, while for the SAP another proposal is suggested as described in section 7.3.1.1
 - Analysis of incident infection will only be performed up to M20 since infection with *P. falciparum* was regularly (monthly) evaluated until this time point.
 - Analysis of prevalent infection will include a model of time to all episodes to have a summary VE measure up to M20 (described in section 7.3.2.1)
 - Additional analysis for endpoints of clinical malaria and incident infection were added mainly to investigate shorter periods (6-monthly post booster dose efficacy7.3.2 (described in section 7.3.2.2).
 - The wording of the impact analyses as planned per protocol has been corrected from "first or only and all episodes" to "all episodes" only (see section 7.3.1.6).
 - The wording of the prevalent *P. falciparum* infections analyses as planned per protocol has been changed to "Prevalent *P. falciparum* infections at each cross-sectional survey" removing "up to Month 14", "up to Month 20", "up to Month 32", "up to Month 38" and "up to Month 50", to improve readability (see section 7.3.1.6).
 - For all episodes analyses fourteen (instead of seven) days following an episode meeting the case definition will be subtracted from the follow-up time, to be consistent with analyses performed in MALARIA-055

